7.3.1.3 Sample Requirements

- a. All samples must be labeled with two unique identifiers and all data should be recorded on the Tissue Studies Form ([Appendix III](#)) including a copy of the pathology report, which must accompany the sample.
- b. For patients with solid tumors:

i. In total, 1 H&E stained slide from all available formalin-fixed paraffin embedded (FFPE) tissue blocks and 15 unstained slides from the most representative block (10 unstained slides will be accepted in cases with limited tissue) or the block itself should be submitted from each surgical procedure (initial diagnosis, post-therapy resection and tumor progression/recurrence [if applicable]). The unstained slides must be from FFPE block(s) for which H&E slides are submitted. From post-therapy resections, unstained slides should include viable tumor if present. Further, if viable tumor is present near margin, these slides should be prioritized to allow for immunohistochemical assessment of isolated tumor cells. These slides will be used for the following analyses:

- Histology review and TRK immunohistochemistry: 1 H&E stained slide from all available formalin-fixed paraffin embedded (FFPE) tissue blocks and 2 unstained slides.
- Fusion sequencing assay: 10 unstained slides derived from formalin-fixed paraffin embedded (FFPE) tissue (5 unstained slides will be accepted in cases with limited tissue).
- Sequencing to identify the fusion breakpoint for ctDNA analysis and to evaluate mechanisms of resistance to TRK inhibition: 3 unstained slides derived from formalin-fixed paraffin embedded (FFPE) tissue

c. For patients with leukemia or solid tumors with bone marrow involvement without suitable FFPE tumor tissue available:

i. In total, 1 Wright Giemsa stained bone marrow aspirate smear, 1 Wright Giemsa stained peripheral blood smear (if available), 1 H&E stained slide from the bone marrow biopsy (if available), 1 H&E stained slide from the clot section (if available), 2 unstained slides from the clot section or core biopsy (if available), and 5-8 unstained bone marrow aspirate smears should be submitted from the baseline bone marrow evaluation and from each bone marrow evaluation while on study. These slides will be used for the following analyses:

- Histology review and TRK immunohistochemistry: 1 Wright Giemsa stained bone marrow aspirate smear, 1 Wright Giemsa stained peripheral blood smear (if available), 1 H&E stained slide from the bone marrow biopsy, 1 H&E stained slide from the clot section (if available), and 2 unstained slides from the clot section or core biopsy.
- Fusion sequencing assay: 2-5 unstained bone marrow aspirate smears.

- Sequencing to identify the fusion breakpoint for ctDNA analysis and to evaluate mechanisms of resistance to TRK inhibition: 3 unstained bone marrow aspirate smears.

7.3.2 Circulating tumor DNA (Optional)

7.3.2.1 Description of Studies

Blood will be collected to evaluate the ability to detect TRK fusions at enrollment, the clearance of detectable circulating tumor DNA (ctDNA) during therapy, and resistance mutations at progression.

7.3.2.2 Sampling Schedule (see Appendix IV)

Plasma samples will be collected in consenting patients at the following time points:

- Post-enrollment, prior to start of protocol therapy
- Cycle 1, Day 15: Prior to AM Larotrectinib dose
- Cycle 2, Day 1: Prior to AM Larotrectinib dose
- Cycle 6, Day 29 (Cycle 7, Day 1 or prior to local control): prior to AM larotrectinib dose
- End of study treatment
- At the time of progression

7.3.2.3 Streck Tube Acquisition

Site personnel should email [contact] and copy the study-assigned ADVL1823 Protocol Coordinator as soon as possible following patient consent to the ctDNA correlative to request Streck tubes. Sites will be sent enough Streck tubes to cover every ctDNA collection time point. Sites should specify their preferred shipping address in their initial email request.

7.3.2.4 Sample Collection and Handling Procedures

For patients who choose to participate in both the ctDNA studies and PK studies, the ctDNA sample should be collected prior to the PK sample on Cycle 1, Day 15 to avoid heparin contamination of the ctDNA sample.

Peripheral blood samples for circulating tumor DNA should be obtained as follows:

- For patients ≥ 10 kg, collect 20 mL (10 ml per tube x 2 tubes)
- For patients ≥ 5 kg but < 10 kg, collect 10 mL (1 tube)
- For patients < 5 kg, collect 5 mL (1 tube)

In all cases, blood draw volumes should strictly adhere to institutional limitations, taking other blood draws into consideration. However, if a reduction in volume is required, samples should be collected in 5 mL increments (i.e., 0, 5, 10, or 20 mL should be collected such that each Streck Cell-Free DNA blood collection tube [BCT] has a minimum of 5 mL).

Established institutional guidelines should be followed for blood collection via vascular access devices. Heparin should be avoided in pre-collection flush procedures. If therapeutic heparin dosing contamination is a possibility, venipuncture is recommended as a first choice collection method. If a Streck Cell-Free DNA BCT tube immediately follows a heparin tube in the draw order, we recommend collecting an EDTA tube as a waste tube prior to collection in the Streck Cell-Free DNA BCT.

For patients who do not have indwelling catheters, blood should be collected via venipuncture. To guard against backflow, observe the following precautions:

- Keep patient's arm in the downward position during the collection procedure.
- Hold the tube with the stopper in the uppermost position so that the tube contents do not touch the stopper or the end of the needle during sample collection.
- Release tourniquet once blood starts to flow in the tube, or within 2 minutes of application.
- Fill tube completely.
- Remove tube from adapter and immediately mix by gentle inversion 8 to 10 times. Inadequate or delayed mixing may result in inaccurate test results.
- Store blood in Streck tube at **room temperature** until shipment.

7.3.2.5 Sample Shipping Instructions

Streck tubes must be labeled with the patient's study registration number, the study I.D., the specimen type (blood) and the date and time the sample was drawn.

Streck tubes should be shipped by FedEx Priority Overnight at **room temperature** to the [name] laboratory for immediate separation, extraction, and storage of plasma and cellular DNA. Samples should be shipped from Monday through Thursday for Tuesday through Friday delivery. If blood is collected in the Streck tube on Friday, over the weekend or on the day before a holiday, the sample can be stored at **room temperature** until shipped on the next business day.

Data should be recorded on the ctDNA Correlative Study Form ([Appendix IV](#)), which must accompany the sample(s).

Ship specimens to the following address:

7.3.3 CSF and Plasma Pharmacokinetics (Required for Patients in Cohort C, N/A for Patients in Cohorts A & B)

7.3.3.1 Description of Studies

Plasma and CSF concentrations of larotrectinib will be determined to evaluate the penetration of larotrectinib across the blood brain barrier in patients having lumbar punctures for intrathecal chemotherapy administration.

7.3.3.2 Sampling Schedule (See Appendix VIII)

CSF samples (0.5 ml) will be collected at the following time points for patients with leukemia:

- First disease evaluation after starting therapy

In addition, CSF samples (0.5 ml) will be collected at the following time points ONLY for leukemia patients receiving intrathecal therapy:

- Cycle 1, Day 8
- Cycle 1, Day 15
- Cycle 1, Day 22

CSF samples will be collected at the time of lumbar puncture. A plasma sample (3 ml) will be obtained as close as possible to the same time as the CSF sample. There is no required time window from the most recent larotrectinib dose, but the dose and time of administration will be recorded. When possible, it is preferred that the lumbar puncture occur >1 hour after the most recent larotrectinib dose.

7.3.3.3 Sample Collection and Handling Instructions

NOTE: Sites are expected to use their own standard materials for PK sample collection. Kits will not be provided for the PK studies for this study.

7.3.3.3.1 CSF Samples

Supplies

- 1 Medium biohazard bag
- 2 Cryovials (2 mL each)
- 1 Plastic transfer pipette
- 2 Cryolabels
- 2 Absorbent Pads

- 1 Federal Express Return Shipping Label (Alturas)
- 1 Dry Ice label
- CSF collection kit
- Alcohol swab for cleansing site
- Dry sterile gauze
- Needle disposal container

Collection Procedure

1. Collect 0.5 mL of CSF using your institution's recommended procedure for standard CSF collection technique. Record the exact time that the sample is drawn along with the exact time that the drug is administered.
2. Complete the cryovial labels with subject ID and visit. Adhere the cryovial labels to each of the cryovials.
3. Divide CSF equally between two cryovials. Screw on the lid.
 - a. Place the labeled cryovials with CSF into an 81-well cryovial box.
4. Immediately transfer the cryovials filled with CSF to a -80°C freezer.
 - a. Only 1 cryovial should be shipped within 1 week to Alturas after each collection. The other should be stored on site in case there is an issue with the first vial.

7.3.3.3.2 Plasma Samples

Collection Procedure

Blood samples (3 ml) will be collected in K₂ EDTA lavender top tubes for PK evaluation. This sample should be collected as close as possible to the same time as the corresponding CSF sample. Record the exact time that the sample is drawn along with the exact time that the drug is administered.

Following collection, the sample will be immediately gently mixed by inversion 8 – 10 times. The sample will be stored on wet ice until centrifugation. The sample will be centrifuged at 1500 x g for 15 minutes at 4° C within 60 minutes after the sample is drawn. The plasma will be transferred to a cryovial, ensuring no RBC contamination, and frozen as soon as possible at -80° C. If a -80° C freezer is not immediately available, the cryovial may be

stored on dry ice for short term storage, but must be placed in the appropriate freezer within 24 hours of the draw-time. The cryovial should be shipped within 1 week to Alturas after each collection.

7.3.3.4 Documentation

1. Ensure the cryovials are properly labeled.
2. Complete the Specimen Submittal Form ([Appendix VIII](#))
3. Complete the dry ice sticker.
 - a. On the day of shipment, fill out the dry ice sticker with the shipper's name, address, and weight of dry ice. Ensure at least 15 pounds (~ 7 kg.) of dry ice for shipment.

7.3.3.5 Sample Shipping Instructions

1. Specimens may be shipped to Alturas, Monday through Wednesday only:

Alturas Analytics, Inc.
[name]
[name]
[contact]
[contact]

2. Obtain a large Styrofoam shipping box of adequate size to hold 15-20 pounds (~7-9 kg.) of dry ice along with the 81-well box containing the frozen cryovials.
3. Fill the Styrofoam shipping box half full (~10 pounds) of dry ice.
4. Transfer samples from the freezer to the dry ice. Ensure the container is sufficiently surrounded by dry ice. Do not allow the samples to thaw.
5. Fill the rest of the container with dry ice. Ensure that the container is sufficiently filled with dry ice (at least 15 pounds) and the samples are completely covered.
6. Place the completed Specimen Submittal Form ([Appendix VIII](#)) inside the cardboard shipping box (but outside the Styrofoam to avoid getting the paper wet). Close and seal shipping box lid with packing tape.
7. Attach the FedEx Return shipping label to the shipper kit box.
 - a. Ensure the **return shipping label for Alturas** is selected for shipping.

8. Attach the dry ice sticker to the shipper kit box.
9. Contact Federal Express for shipment ([name] or [name]; toll free in the US).
10. Email a copy of the Specimen Submittal Form ([Appendix VIII](#)) to the following email addresses:

[REDACTED]
[contact]
11. Include the Protocol ID, Patient ID, and FedEx Tracking Number in the email. Please write the tracking number without spaces (i.e. Correct= 000100020003; Incorrect = 0001 0002 0003).

7.4 Imaging Central Review

Central imaging review will be conducted for all imaging through Cycle 6. Additional central review of imaging evaluations performed for study participants during therapy or follow up on individual basis will occur as determined by the study committee and study radiologist. COG Operations Center will notify the Imaging Research Center of any patient requiring central review. The Imaging Research Center will then request that the treating institution forward the pertinent images for central review. The central image evaluation results will be entered into Rave for review for data analysis. Central imaging review will be performed retrospectively and will not be used to guide individual patient management.

The images are to be forwarded electronically to the Imaging Research Center at Children's Hospital Los Angeles via the ImageInBox.

COG institutions that are not connected via the ImageInBox can send the images on hard copy film, CD ROM, DVD, USB flash drive or by FTP. Submitted imaging studies should be clearly marked with the COG patient ID, study number (ADVL1823) and date, and shipped to [name] at the address below:

[name], CCRP
Administrator, Imaging Research Center
Children's Hospital Los Angeles
[name]
[name]
[contact]
[contact]
Email: [contact]

8.0 CRITERIA FOR REMOVAL FROM PROTOCOL THERAPY AND OFF STUDY CRITERIA

8.1 Criteria for Removal from Protocol Therapy

- a) Clinical (including physical examination or serum tumor markers) or radiographic evidence of progressive disease or treatment failure while on study (See [Section 10.3.3](#), [Section 10.5.2](#), [Section 10.5.3](#), [Section 10.6.6](#), and [Section 10.7.5](#)).
- b) Adverse Events requiring removal from protocol therapy, as stated in [Section 5.0](#).
- c) Patients who receive concurrent investigational therapy or anticancer therapy, as stated in [Section 3.3.2.3](#) and [Section 3.3.2.4](#).
- d) Refusal of further protocol therapy by patient/parent/guardian.
- e) Physician determines it is in patient's best interest.
- f) Repeat eligibility studies (if required) are outside the parameters required for eligibility prior to the start of larotrectinib ([Section 3.2.6](#)).
- g) Non-compliance that in the opinion of the investigator does not allow for ongoing participation.
- h) Patients who develop a second malignant neoplasm.
- i) Study is terminated by sponsor.
- j) Pregnancy
- k) Completion of planned therapy per [Section 4.1](#).
- l) Patients with leukemia who have persistent CNS disease that does not clear by the end of Cycle 1.

Patients who are removed from protocol therapy are to be followed until they meet the criteria for Off Study ([Section 8.2](#)). Follow-up data will be required unless consent was withdrawn.

8.2 Off Study Criteria

- a) Death.
- b) Lost to follow-up.
- c) Patient enrollment onto another COG anti-cancer therapeutic study (e.g., at recurrence).
- d) Withdrawal of consent for any further data submission.
- e) The fifth anniversary of the date the patient was enrolled on this study.
- f) The patient does not receive protocol treatment after study enrollment.

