1.2 Secondary Aims

- 1.2.1 To determine event-free survival (EFS), overall survival (OS), and duration of response (DoR) of children with IFS treated with neoadjuvant larotrectinib prior to local control.
- 1.2.2 To determine the ORR, EFS, OS, and DoR of children with newly diagnosed TRK fusion solid tumors other than IFS treated with neoadjuvant larotrectinib prior to local control.
- 1.2.3 To describe the toxicity of larotrectinib in children with solid tumors and acute leukemia.
- 1.2.4 To determine the percentage of patients with TRK fusion solid tumors with detectable circulating tumor DNA at baseline and after 2 weeks, 4 weeks, 24 weeks of treatment, at the time of discontinuation of larotrectinib therapy, and at progression.

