1.3 Exploratory Aims

- 1.3.1 To determine the EFS, OS, and DoR of children with TRK fusion solid tumors other than IFS treated with adjuvant larotrectinib following upfront surgery with positive margins after neoadjuvant larotrectinib.
- 1.3.2 To determine the EFS, OS, and DoR of children with TRK fusion solid tumors who experience a complete response to larotrectinib and subsequently discontinue larotrectinib therapy
- 1.3.3 To determine the remission induction rate for patients with recurrent/refractory TRK fusion leukemia when treated with larotrectinib.
- 1.3.4 To evaluate the surgical morbidity and extent of resection of initially unresectable tumors in patients with TRK fusion solid tumors who undergo surgical resection following neoadjuvant larotrectinib.
- 1.3.5 To evaluate mechanisms of response and resistance to larotrectinib in children with TRK fusion cancers.
- 1.3.6 To evaluate the morphologic features of TRK fusion solid tumors at time of initial

biopsy to further define criteria for pathologic diagnosis of these tumors.

- 1.3.7 To evaluate immunohistochemistry for pan-TRK as a screening method for TRK fusion tumors and in resection specimens following neoadjuvant treatment with larotrectinib.
- 1.3.8 To evaluate the histologic response to larotrectinib in resection specimens following neoadjuvant treatment.
- 1.3.9 To evaluate circulating tumor DNA for the detection of the emergence of resistance mutations and recurrence in patients with TRK fusion solid tumors treated with larotrectinib.
- 1.3.10 To evaluate the ratio of CSF to concurrent plasma concentrations of larotrectinib in patients with leukemia.
- 1.3.11 To evaluate the change in neurocognitive/behavioral functioning over time between baseline and 5 years post-diagnosis of patients treated on this protocol using parent-reported adaptive functioning (ABAS-III General Adaptive Composite), executive function (BRIEF-P or BRIEF-2 Global Executive Composite Score), psychosocial functioning (BASC-3 Internalizing, Externalizing and Behavioral Symptoms Indices) and quality of life (PedsQL Total score).

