3.0 ENROLLMENT PROCEDURES AND ELIGIBILITY CRITERIA

3.1 Study Enrollment

3.1.1 Patient Registration

Prior to enrollment on this study, patients must be assigned a COG patient ID number. This number is obtained via the Patient Registry module in OPEN once authorization for the release of protected health information (PHI) has been obtained. The COG patient ID number is used to identify the patient in all future interactions with COG. If you have problems with the registration, please refer to the online help. For additional help or information, please contact the CTSU Help Desk at [name] or [contact].

In order for an institution to maintain COG membership requirements, every patient with a known or suspected neoplasm needs to be offered participation in APEC14B1, *Project: Every Child A Registry, Eligibility Screening, Biology and Outcome Study*.

A Biopathology Center (BPC) number will be assigned as part of the registration process. Each patient will be assigned only one BPC number per COG Patient ID. For additional information about the labeling of specimens please refer to the Pathology and/or Biology Guidelines in this protocol.

Please see [Appendix I](#) for detailed CTEP Registration Procedures for Investigators and Associates, and Cancer Trials Support Unit (CTSU) Registration Procedures including: how to download site registration documents; requirements for site registration, submission of regulatory documents and how to check your site's registration status.

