7.2 Follow-up

| STUDIES TO BE OBTAINED | While in Follow-up after Completion of Planned Therapy per Section 4.1 ¹ | While in Follow-up for Other Reasons ⁶ |
|---|---|---|
| History, including any anti-cancer therapy received | X ² | X |
| Physical exam with VS, including neurologic examination | X ² | X |
| Ht, Wt, BSA | X ² | X |
| Disease evaluation | X ² | X |
| Circulating tumor DNA | X ³ | |
| Tumor tissue submission | X ⁴ | X ⁴ |
| Neurocognitive assessments | X ⁵ | |

¹ Patients who have progressive disease while in Follow-up after completion of planned therapy will be subsequently monitored per the table for patients in Follow-up for other reasons.

² At 3, 6, 12, 18, 24, 30, 36, and 48 months after discontinuation of larotrectinib, and annually thereafter for up to 5 years from the date of study entry. Studies may be obtained \pm 14 days of the indicated timepoint.

- ³ See [Section 7.3.2](#) for timing of circulating tumor DNA (ctDNA) studies. For patients in Follow-up, ctDNA will be obtained at the time of progression.
- ⁴ Submission of tumor tissue from any biopsy after progression is optional.
- ⁵ See [Appendix XI](#). For patients in Follow-up, neurocognitive tests will be obtained 6 months (\pm 4 weeks) after enrollment, 12 months (\pm 4 weeks) after enrollment, 24 months (\pm 4 weeks) after enrollment, and 4-5 years after enrollment. Timing should be based on enrollment, regardless of whether the patient is receiving larotrectinib or is in Follow-up.
- ⁶ Follow-up for patients who discontinue therapy on this study for reasons other than completion of planned therapy ([Section 8.0](#)) is required at 30 days, 6 months, and 12 months from the last date of protocol therapy, and annually thereafter for up to five years from the date of study entry.

See COG Late Effects Guidelines for recommended post treatment Follow-up:
<http://www.survivorshipguidelines.org/>

Note: Follow-up data are expected to be submitted per the Case Report Forms (CRFs) schedule.

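### Criterion 8.2(c) ends follow-up when a child joins another COG treatment study, for example at recurrence, so OS censoring is likely informative and OS is expected, though not certain, to read too high

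*Combined protocol and SAP*

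**What the plan says.** Section 8.2, item (c), takes a patient off study on "Patient enrollment onto another COG anti-cancer therapeutic study (e.g., at recurrence"). Section 8.1 defines what going off study ends: "Patients who are removed from protocol therapy are to be followed until they meet the criteria for Off Study".

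Section 7.2 sets out a longer plan. Patients who stop therapy early are seen at 30 days, 6 months and 12 months, then "annually thereafter for up to five years from the date of study entry". Those who progress after completing planned therapy "will be subsequently monitored per the table for patients in Follow-up for other reasons". Both columns of the 7.2 table ask for a history that covers anti-cancer therapy received, so follow-up is meant to continue through later treatment. That section makes no exception for another COG study.

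OS is named in aim 1.2.1 ("To determine event-free survival (EFS), overall survival (OS), and duration of response (DoR) of children with IFS") and aim 1.2.2 ("To determine the ORR, EFS, OS, and DoR of children with newly diagnosed TRK fusion solid tumors other than IFS"), and again in exploratory aims 1.3.1 and 1.3.2. Section 9.3 says when OS will be computed (one year after the last enrollment in a stratum). It gives no OS definition, no OS censoring rule and no sensitivity analysis. No section provides for collecting vital status, or linking survival data from a later COG study, once a patient is off study.

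**The concern.** Take a child who progresses and then enters a COG relapse study. Read literally, 8.1 and 8.2(c) end follow-up on that date. If OS is then censored at last contact, a later death does not enter this trial's OS. The usual estimators assume that a censored child has the same outlook as those still at risk, who here are mostly relapse-free. Because 8.2(c) gives recurrence as its own example, that assumption is doubtful exactly where the rule applies.

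At stake is a secondary endpoint in small cohorts, where a few unseen deaths change the estimate visibly. Nothing in Section 9 would detect or correct the loss. The stated rule causes it, so this is more than a detail left unwritten.

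**Working it through.** **Plan's own figure.** The plan gives no OS sample size, event count or precision. Its only design calculation is the two-stage rule for ORR (9 then 12 more patients; continue with 6 or more responses, success with 16 or more of 21). With X ~ Bin(9, p) and Y ~ Bin(12, p), the success probability is the sum over x = 6 to 9 of P(X = x) × P(Y ≥ 16 − x). This gives 0.0905 at p = 0.60 and 0.9040 at p = 0.85. Early termination at p = 0.60 has probability 0.5174, and the expected sample size is 14.79. All match Section 9.2. Best response is judged within six cycles, so this rule does not depend on survival follow-up.

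**One hidden death.** In a cohort of 21, 1/21 = 4.8 points: crude OS of 20/21 = 95.2% would be reported as 100%.

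**Inputs for an illustration.**
- IFS relapse fraction r: Section 2.1.2 gives 7 events in 27 Group 3 patients, 7/27 = 26% (EFS 74%). This is a chemotherapy figure.
- IFS true OS: Section 2.1.2 gives 80–100%; 80%, 90% and 97% are used.
- CMN-like: Section 2.1.3 gives 4 relapses and 1 death in 18 fusion-positive patients, so true OS = 17/18 = 94.4%.
- Sarcoma-like: Section 2.1.4 gives 4-year EFS of 49%. It is assumed that half of relapsed patients die, so true OS = 1 − 0.51 × 0.5 = 74.5%.
- Share q of relapsed children who join another COG study: not in the documents. Assumed 25%, 50% and 100%.
- Further assumptions: every death follows relapse; relapse falls uniformly between 0.2 and 3 years and death 0.1 to 2 years after it; joiners are censored at relapse and have the same risk of death as other relapsed children.

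**Results.** Kaplan-Meier 5-year OS minus true OS, in points, from 400,000 simulated patients per scenario:

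| Setting | True OS | q = 25% | q = 50% | q = 100% |
|---|---|---|---|---|
| IFS-like | 97% | +0.6 | +1.3 | +3.0 |
| IFS-like | 90% | +2.1 | +4.5 | +10.0 |
| IFS-like | 80% | +4.2 | +8.8 | +20.1 |
| CMN-like | 94.4% | +1.2 | +2.5 | +5.6 |
| Sarcoma-like | 74.5% | +4.1 | +9.3 | +25.4 |

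**Hand check.** If all joining came before any death, the estimate would be 1 − (1 − q)d/(1 − qr), with d = 1 − true OS. For d = 0.10 and r = 0.26, q = 25% gives 1 − 0.075/0.935 = 0.920, and q = 50% gives 1 − 0.05/0.87 = 0.943. The simulation gives 0.921 and 0.944. At q = 100% every death is hidden and the bias is simply d.

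**Direction is not guaranteed.** Suppose 3 of 21 children relapse, join another COG study, are censored at year 1 and all survive, while one other child dies at year 2. True OS is 20/21 = 95.2%. Kaplan-Meier gives 17/18 = 94.4%, which is lower.

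**The case against.** The strongest textual reply is the closing sentence of Section 8.1, which keeps follow-up data due unless consent has been withdrawn. It might be read as overriding 8.2(c). It does not clearly do so: the sentence before it ends follow-up at any off-study criterion, and 8.2 lists (c) separately from withdrawal of consent (d). At best the sections conflict and sites may apply them differently.

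A second reply is that the cooperative group can link records. Section 3.1.1 says "The COG patient ID number is used to identify the patient in all future interactions with COG", and a registry and outcome study must be offered to every patient. The means exist, but no section plans the linkage or its use for OS, and registry participation is offered, not required.

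Several limits stand. Only COG therapeutic studies trigger (c); children treated off study or on other trials stay in follow-up. Relapse need not lead to a new trial: Section 2.4.1 describes a patient who progressed off larotrectinib, restarted it and responded. No OS test or comparison with the historical 80–100% is planned. That range describes IFS generally, whereas this trial excludes disease resectable without significant deficit.

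Three stronger readings are tempting and unsupported:
- A reader might infer that the rule can only raise OS. The counterexample above shows otherwise.
- A reader might infer that it also costs the 4–5 year neurocognitive data. The 7.2 table leaves that row blank for patients in follow-up for other reasons, the column to which progressing patients move. Their assessments may be lost regardless. Any tension with Section 3.1.7 is a separate matter.
- A reader might pick one scenario in which a true OS near 90% is reported as 100%. The inputs for any single scenario are not in the documents, so only a range is defensible.

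**Conclusion.** The concern holds in a limited form. Sections 8.1 and 8.2(c), read together, end follow-up at a moment tied to relapse, while 7.2 plans to continue to five years and OS is a secondary aim. The resulting censoring is likely informative, and upward bias is the expected direction but not a certain one.

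The size is unknown. For IFS the illustration ranges from under 1 point to about 20, and from +2.1 to +10.0 at a true OS of 90%. It may be small in Cohort A and larger for sarcoma-like tumors in Cohort B. Under the model's assumption that all deaths follow relapse, the bias is zero if no relapsed child joins or none dies.

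All of this rests on the assumed joining shares and on historical relapse rates from other treatments. It also uses a 5-year horizon that Section 9.3 does not specify. Bias at the planned analysis, one year after last enrollment, was not computed. Section 9.3 names no estimator; Kaplan-Meier is assumed here, but any method that treats this censoring as non-informative is exposed.

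The ORR decision is unaffected. EFS and DoR are largely spared, because a child who joins at recurrence has already had the event.

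**What to change.** - **Section 8.2(c):** limit it to stopping study visits and procedures.
- **Vital status:** for every treated patient, keep collecting date of last contact, vital status and date of death to the fifth anniversary of enrollment, unless consent for data submission is withdrawn under 8.2(d). Take these from the later COG study or the registry, through the COG patient ID, where consent allows.
- **Sections 7.2, 8.1 and 8.2(c):** reconcile them so that a site can tell which data remain due.
- **Section 9.3:** define OS and state that it is not censored at entry to another COG study. Report how many patients met 8.2(c). For any whose vital status is not recovered, add a worst-case sensitivity analysis that counts them as deaths.

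The cost is a small annual data pull within one cooperative group, with no new visits or procedures. Section 2.7.1 says accrual is complete, so patients already off study under (c) would need consent or authorization checks before their data are retrieved, and recovery may be incomplete. If vital status is obtained for all of them, this source of bias disappears.
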